2.1.2 Secondary Objectives

- To determine, in comparison to usual care, whether usual care augmented by intra-dialytic exercise training improves the physical function of stage 5 CKD patients receiving maintenance haemodialysis renal replacement therapy
- ii. To compare the effect of usual care augmented intra-dialytic exercise training versus usual care on systemic and biochemical markers of vascular and cardio-metabolic health of stage 5 CKD patients receiving maintenance haemodialysis renal replacement therapy
- To assess, in comparison to usual care, whether usual care augmented by intra-dialytic exercise training is associated with an excess of adverse events in stage 5 CKD patients receiving maintenance haemodialysis renal replacement therapy

- iv. To explore and document the views of participants and members of the renal care teams in relation to their experiences of usual care and intra-dialytic exercise-augmented usual care
- v. To estimate the cost-effectiveness of augmenting, with intra-dialytic exercise training, the usual care stage of 5 CKD patients receiving maintenance haemodialysis renal replacement therapy

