2.1.4 Secondary Endpoint

Assessed at 6, 9 and 15 months. Change between baseline and follow-up for:

- KDQOL-PCS
- KDQOL-MCS
- KDQOL-Vitality subscale
- KDQOL- symptom burden subscale
- IPAQ
- Height (at screening visit only), Weight and anthropometric (BMI, waist to hip ratio)
- Peak aerobic capacity
- Duke Activity Status Index (self-report 12-item activity of daily living questionnaire)
- 10m Timed-up-and-go (composite test of leg strength, balance, coordination and gait speed)
- Sit-to-stand 60 (proxy measure of lower extremity muscular endurance)
- Tinetti Falls Efficacy Scale
- Habitual physical activity (a self-report assessment via International Physical Activity Questionnaire)
- Habitual physical activity (GT3X tri-axial accelerometer)
- Arterial stiffness (via pulse wave velocity and augmentation index)
- Blood pressure
- Hb
- ESAs
- Phosphate
- Parathyroid hormone (PTH)
- EQ-5D, a generic multi-attribute health related QOL questionnaire for use in cost utility analysis.
- Health Economic questionnaire regarding resource use
- All hospitalisations
- All-cause mortality
- Cardiovascular mortality
- Safety / Harms (SAE)

Qualitative Study and analysis

A constructivist phenomenological approach will be used to learn about views and perceptions of participants and build greater understanding of varied perspectives of both service users and providers (Crotty 1998; Grbich 1999). Focus groups and individual interviews will be used as most appropriate to the stage of the study and location of data collection. All participants in the pilot study and RCT will be eligible for inclusion in the qualitative sub-study. Purposive sampling will be used to ensure varied experiences and viewpoints are represented, for example, including service users and providers from different study regions, including people in both study arms, and aiming to include people with different participation rates and response to the intervention. Appropriate topic guides will be developed for pilot study and RCT, and for service users and providers; questions will be discussed within the project team and steering group.

Health Economic analysis

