To maximise relevance to policy, the health economic evaluation will follow the quidelines recommended by NICE, including the use of cost-utility analysis and adopting an NHS costing perspective. Quality adjusted life years (QALYs) will be derived from utility scores generated using a standard UK algorithm from the EQ-5D. Resource use associated with physiotherapy assistant time and [training in use of equipment and delivery of personal exercise programmes per patient] time will be recorded prospectively using timesheets for the intervention group. Equipment costs will be calculated using the annuity method with discounting rates set as per NICE base case]. Other health care resource use will be captured through patient questionnaires administered monthly during dialysis sessions. Factors to be measured have been extracted from the literature and consultation with experts and include (but are not limited to): primary care consultations, nephrologists consultations, calls to NHS Direct/NHS24, accident and emergency visits, NHS provided devices and aids and Physiotherapy sessions. During the internal pilot phase a free format "other" category will be included to check for omitted items. Additionally, hospital admissions and medication use will be recorded (with consent) from nephrologists' records. Resource use estimates will then be combined with standard UK sources to estimate total NHS costs.

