4.6 Schedule of Assessment for each visit

Table 2. The range and phasing of PEDAL study assessment procedures

ASSESSMENT PROCEDURES					
	Timeline ± 1 week				
	Screening	Baseline	6 months	9 months	15 months
Informed Consent	X				
Inclusion/Exclusion Criteria	Х				
Medical History/Demographics	Х				
Adverse Events Recorded		Х	Х	Х	Х
Review/Record Medication		Х			
Anthropometric Measurements					
Height		Х	Х	Х	Х
Weight		Х	Х	Х	Х
Body Mass Index		Х	Х	Х	Х
Waist-to-Hip ratio		Х	Х	Х	Х
Quality of Life (and symptom					
burden) Assessments)					
* KDQOL		Х	Х	Х	Х
* EQ5D		Х	Х	Х	Х
Cardiovascular Assessments					
Resting Heart Rate		Х	Х	Х	Х
Resting Blood Pressure		Х	Х	Х	Х
Pulse Wave Velocity		Х	Х	Х	Х
Augmentation Index		Х	Х	Х	Х
Functional Capacity					
Measurements					
Peak Aerobic Capacity		Х	Х	Х	Х
(VO ₂ peak and/or Peak power output)					
Sit-to-Stand 60		Х	X	Х	Х
Functional Mobility (10mTUG)		Х	Х	Х	Х
* DASI questionnaire		Х	Х	Х	Х
* Tenetti Falls Efficacy Scale		Х	Х	Х	Х
Habitual Physical Activity					
GT3X Accelerometer		Х	Х	Х	Х
International Physical Activity		Х	Х	Х	Х
Questionnaire					
Routine Clinical Chemistry					
URR(5)		Х			
Blood lipid levels		X			
(LDL, HDL, triglyceride levels)					
Hb (and ESAs)		Х	Х	Х	X
HBA1c		X			,,
CRP		X			
Bicarbonate		X			
Phosphate		X	Х	Х	Х
Parathyroid hormone		X	X	X	X
		l			
Note: * o	denotes patient	t-reported out	come.		

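### Patient-reported resource use is collected only at dialysis sessions, so these cost items stop for participants who are transplanted or otherwise leave in-centre haemodialysis

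*Protocol*

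**What the plan says.** Secondary objective v (Protocol section 2.1.2) is "To estimate the cost-effectiveness of augmenting, with intra-dialytic exercise training", compared with usual care. The Health Economic analysis text under section 2.1.4 names three sources of resource-use data:

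- **Patient questionnaires:** "Other health care resource use will be captured through patient questionnaires administered monthly during dialysis sessions". The items listed, not exhaustively, are primary care and nephrologist consultations, telephone advice lines, emergency attendances, aids and devices, and physiotherapy.
- **Clinical records:** "Additionally, hospital admissions and medication use will be recorded (with consent) from nephrologists' records".
- **Staff timesheets:** physiotherapy assistant time and training time "will be recorded prospectively using timesheets for the intervention group".

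The endpoint list in the same section is headed "Assessed at 6, 9 and 15 months. Change between baseline and follow-up for" and includes "Health Economic questionnaire regarding resource use". Table 2 in section 4.6, titled "The range and phasing of PEDAL study assessment procedures", has EQ5D at baseline and at all three follow-up visits, but no resource-use row.

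Section 7 has study questionnaires completed at assessment visits, giving KDQOL and EQ-5D as examples. If a visit is missed, they are handed out during dialysis. Section 4.5.2 says all enrolled patients will be followed for an intention-to-treat analysis. Section 6.6 expects 17-25% to stop the exercise programme over 9 months, and transplant is one of the reasons given.

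**The concern.** The protocol ties the patient-reported part of the cost data to attendance at a dialysis session, yet expects some participants to stop attending while still in follow-up. From that point no route is stated for these items. The assessment visits take place on non-dialysis days (section 4.8.2), so EQ-5D can continue for the same people. Their quality-adjusted life years could then be observed for a period in which part of their cost is not.

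The loss follows a change of treatment modality, and a patient's use of services after a transplant may well differ from use while on haemodialysis. Data missing for that reason are unlikely to be missing at random. An analysis plan can say how to handle missing costs, but it cannot recover forms that were never given.

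**Working it through.** The protocol states no figure on this point, so there is none to reproduce. The check compares the texts and then sizes the exposure.

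**1. Which cost components depend on a dialysis session?**

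| Component | Stated source | Needs a dialysis session? |
|---|---|---|
| Consultations, advice calls, emergency visits, aids, physiotherapy | Monthly patient questionnaire | Yes |
| Hospital admissions, medication | Nephrologists' records, with consent | No |
| Exercise delivery and training time | Timesheets | No |

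Only the first row is exposed.

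**2. Is there another route for the first row?** Section 7 does not name the resource-use form among the questionnaires done at assessment visits, so it neither clearly supplies a route nor rules one out. Its fallback for a missed visit again needs a dialysis session.

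**3. Who is exposed?** Participants who are alive, still consenting and no longer on in-centre haemodialysis. Someone who stops cycling by choice still attends dialysis and still receives the form. Someone who dies has no later costs to record.

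**4. How many?** The protocol does not say. Two assumed ranges:

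- Directly, 5-10% of those randomised: 380 × 0.05 = 19 and 380 × 0.10 = 38.
- As a share of expected discontinuers: 380 × 0.17 = 64.6 and 380 × 0.25 = 95. If one third to two thirds of these leave in-centre haemodialysis alive: 64.6 × 1/3 ≈ 22 up to 95 × 2/3 ≈ 63. This range applies the exercise-programme rate to both arms, as section 6.6 does when it assumes similar discontinuation under usual care. The upper end is generous, because the rate includes death and personal choice.

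**5. How much of each person's data?** No end month is given. If monthly collection runs to month 15 there are 15 forms; if it stops with the intervention there are 9. Taking 15, a participant who leaves at month 6 loses 15 − 6 = 9 forms (9/15 = 60%), and one who leaves at month 9 loses 6 (6/15 = 40%). With 5-10% leaving, the share of all planned forms lost is 0.05 × 0.40 = 2% at the low end and 0.10 × 0.60 = 6% at the high end. The departure months are illustrative.

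**6. The two timings.** The endpoint list gives 3 follow-up points with a longest gap of 6 months; the Health Economic analysis text gives monthly forms. The heading over the list also covers hospitalisations, mortality and serious adverse events, which accrue continuously. Monthly forms summed to months 6, 9 and 15 are compatible with both texts, but the protocol does not say that this is what is meant.

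**The case against.** The strongest reply is that most of what matters for cost is safe. Admissions, medication and the cost of the intervention do not depend on a dialysis session. This stands: a reader might infer that participants who leave haemodialysis lose all later resource-use data, and the source table shows that they do not.

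A second reply is that few participants will leave. Section 3.3 excludes patients likely to receive a live-donor transplant or move to peritoneal dialysis within about 6 months, and the 17-25% concerns the exercise programme, not dialysis. This limits the number but does not remove it: section 6.6 itself expects transplants, and follow-up runs to 15 months.

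A third reply is that similar discontinuation is assumed in both arms, so the loss may be balanced. That is fair. Nothing in the protocol shows a difference between arms or a direction of bias.

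A reader might also infer a flat contradiction between monthly and 6, 9 and 15 month collection, and conclude from the missing Table 2 row that sites would never give the form. Neither inference is supported. The endpoint heading can be read as reporting times. Table 2 has columns only for screening, baseline and the three follow-up visits, so a monthly form has no place in it. Hospitalisations and mortality have no row either, and the Health Economic analysis text states the monthly form explicitly. Nor does the protocol plan to analyse costs as change from baseline in any worked-out sense: the same text aims at total NHS costs.

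**Conclusion.** The point holds for the patient-reported items only. As written, their collection has no stated route once a participant leaves in-centre haemodialysis, which does not fit the promise to follow everyone. The size is modest and uncertain: about 19-38 participants if 5-10% leave alive, and roughly 2-6% of planned forms if they leave between months 6 and 9 and collection runs to month 15. The leaving rate, the departure months and the 15-month period are all assumptions; the protocol gives no leaving rate and no costing horizon.

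The loss depends on modality and is unlikely to be random, but bias in cost per quality-adjusted life year, in either direction, is not demonstrated. The primary endpoint is unaffected. The relation between the two timings, the absent schedule entry and the unstated end month are matters of clarification and would not justify a finding alone.

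**What to change.** In the Health Economic analysis text under section 2.1.4, state that participants no longer on in-centre haemodialysis complete the same resource-use questionnaire by post or telephone, on the same dates and in both arms, with recall running from the last completed questionnaire. That recall period also lets a late form cover a missed month.

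As clarifications in the same edit:

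- State that the monthly data are summed to months 6, 9 and 15 and are not analysed as change from baseline.
- State the month in which collection ends.
- Add a line or footnote to Table 2 pointing to the monthly form.

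The cost is a few sentences of wording and a small number of extra forms handled by existing staff. Section 4.8.2 already uses letters and telephone contact for visit reminders, so the means are in place.

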2.2 Study Design

The PEDAL study is designed as a pragmatic, multicentre RCT (with an internal pilot study) with two treatment arms: intra-dialytic exercise training plus usual care maintenance haemodialysis (EXHD) versus usual care maintenance haemodialysis (UCHD). Participants' QOL and functional limitations will be assessed prior to treatment randomisation and after 6, 9 and 15 months. The primary endpoint will be after 6 months with additional follow-up at the end of the intervention (9 months) and again 6 months after the end of the intervention period. It will be impossible to blind the "treating" physiotherapy assistants or the participants and thus the study will undertake blinded outcome assessment and analysis. We propose to recruit participants to the PEDAL study from all eligible adult prevalent HD patients who have been receiving maintenance HD for more than 3 months. These will be recruited from UK (outpatient in-centre) HD units. Recruitment for the trial will take place over a 21-month period between November 2014 and July 2016 in HD units

based in 10 sites across 5 regions of the United Kingdom (London, Birmingham/West Midlands, East Midlands, North Wales & North West England, and Central Scotland)

[figure not shown]

2.3 Study Scheme Diagram

Flow diagram

Figure 1. Flow of participants through the study

3. Subject Selection

3.1 Number of Participants

The total study duration will be 48 months and will involve 380 participants; 190 of whom will be randomly allocated to receive usual care maintenance haemodialysis renal replacement therapy (as described in section 4.5.1) and 190 randomly allocated to receive usual care augmented by intra-dialytic exercise training (as described in section 4.5.2). Further details of sample characteristics and desired statistical power are described respectively in sections 4.1 and 6.6. Figure 1, above, summarises the estimated percentage proportions, and absolute recruitment numbers, for participant availability, eligibility and participant flow through the PEDAL study. The key milestones for this proposed study are outlined in Table 1.

Table 1. PEDAL Trial milestones

Month 0 -6	Recruitment of Staff			
	Staff training (SOP for outcome assessments			
	and exercise training, eCRF)			
	Outstanding Ethics amendments/approvals			
	and R & D approval			
	Finalising the set-up of research sites			
Month 7	Recruitment of first participants			
Month 13	Follow-up assessments begin			
Month 13	Submission of protocol paper for publication			
Month 18	Internal pilot data evaluation			
Month 19	Report to Steering Committee and DMC for			
	interim review			
Month 28	Recruitment ends			
Month 42	End of follow-up			
Month 42	Production of Qualitative study Report			
Month 42	Closure of all databases			
Month 48	Draft report and Draft papers submitted			

3.2 Inclusion Criteria

- Prevalent Stage 5 CKD patients (GFR <15 mL/min) receiving maintenance haemodialysis therapy for more than 3 months
- Male or female
- Aged >18 years
- Able to provide written informed consent

3.3 Exclusion Criteria

- Patients unlikely to be on HD for > 6 months (this includes cachectic patients, those with severe heart failure, patients in whom dialysis withdrawal is being considered, and patients likely to receive a live-donor transplant or transfer to PD in that period of time)
- Less than 3 months after the initiation of haemodialysis (patients in this time-frame are generally less clinically stable, many having vascular access procedures performed, and rates of inter-current events, including death and hospitalisation, are very much higher in the first 3 months after commencement of chronic haemodialysis)
- Deemed to be clinically unstable by treating physician
- Bilateral lower limb amputees
- Dementia or severe cognitive impairment (as will be unable to give consent and/or complete questionnaire assessments)
- Severe psychiatric disorders except treated stable
- Pregnancy

4. Study Procedures

4.1 Identifying Participants

Prevalent adult patients (aged 18+), treated as outpatients, undergoing in-centre (hospital unit, satellite unit) renal replacement therapy via maintenance haemodialysis. Patients who are naive to intra-dialytic exercise will be recruited from HD units across the five participating "regions". A number of exclusion criteria apply, and these are listed in section 3.3 above. The majority of potential participants for the PEDAL study will be identified during routine haemodialysis management consultations and concurrent evaluation of patient (clinical) notes to confirm eligibility for participation. Patients already established on haemodialysis for more than 3 months will be eligible and are easily identified from hospital databases and dialysis logs. If considered potentially eligible for the study, they will be approached by a member of the renal care team who will discuss the study with them and leave them a Patient Information Sheet (PIS) to read with further details.

The sample will be obtained from ~10 recruitment sites organized into five "regions" spread across the UK. The research sites selected are considered broadly representative of contemporary UK haemodialysis units and geographically cover a wide range of the UK (Glasgow/Lanarkshire, Salford/North Wales, Derby/Nottingham, Birmingham/Heart of England Trust, London). These centres have been selected as they also provide access to large numbers of prevalent HD patients. Figure 1 summarises participant flow through the study. Using UK Renal Registry data from

2010 (1) we estimate there to be approximately 3800 eligible prevalent patients for this study. We are allowing for the potential loss of approximately 40% of these eligible patients due to their enrolment in other clinical trials with potentially confounding effects upon study outcomes in the PEDAL trial. In addition, we have conservatively employed a 20% consent/participation rate in all of our sample estimates leaving a potentially recruitable sample pool of around 440 prevalent patients. We intend to recruit 380 patients to meet the study objectives with a target rate of 18 participants per month entering the trial across the 21 month recruitment period.

4.2 Informed Consent Procedures

After allowing the patient a minimum of 24 hours to read and digest the information in the PIS, and to consult with family members, the research team will approach the patient (usually during the next dialysis session) and be available to answer any questions. If the patient is happy to proceed, an appointment will be made for familiarisation and baseline outcome assessment sessions. Informed consent may be obtained by any member of the research team, including the Principal Investigator, sub-investigator, research nurse, research assistant, research coordinator, or physiotherapy assistant.

4.3 Screening for Eligibility

After informed consent is obtained and eligibility by all the criteria (protocol sections 3.2 & 3.3) confirmed, study assessments as outlined in section 4.6 will be performed.

4.4 Randomisation and Treatment Allocation

Randomisation will be via a centrally controlled web-based GCP compliant randomisation system, run by Glasgow Clinical Trials Unit (GCTU). To ensure balanced assignment across critical variables, a minimisation algorithm will be employed, using baseline age, sex and diabetic status.

Participants will be allowed to continue all their usual medication throughout.

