
We propose to employ physiotherapy assistants (PA, band 4 technical Instructors) in each region to deliver the intra-dialytic intervention. All PAs will be trained by the joint PI and regional coordinators, on how to standardise the delivery of the exercise prescription as well as how to record exercise prescription milestones, compliance behaviours, and any adverse outcomes. The proposed exercise intervention delivered this way would ensure appropriate and consistently applied progression of both the duration and intensity of the exercise training. Recent evidence from the British Renal Society Symposium revealed that successful patient compliance with and the effectiveness of intra-dialytic exercise training was enhanced by the involvement of a physiotherapy assistant in programme delivery (34). This role, supervised and quality assured by the regional coordinator, involves the technical implementation of the exercise prescription and associated protocols produced by the regional Research Assistant who will be blinded to treatment allocation.

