5.3.2 Assessment of causality

Probable: A causal relationship is clinically / biologically highly plausible and there is a plausible time sequence between onset of the adverse event and the exercise intervention.

Possible: A causal relationship is clinically / biologically plausible and there is a plausible time sequence between onset of the adverse event and the exercise intervention.

Unlikely: A causal relationship is improbable and another documented cause of the adverse event is most plausible.

Unrelated: A causal relationship can definitely be excluded and another documented cause of the adverse event is most plausible.

6. Statistical Considerations

Analysis and reporting of this trial will be based on Consolidated Standards of Reporting Trials (CONSORT) guidelines with the analyses conducted on an intention-to-treat basis. Descriptive statistics of clinical and socio-demographic variables at baseline will be presented. All treatment comparisons will be adjusted for the minimisation variables (diabetic status, age and gender).

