6.1 Primary Outcome

KDQOL PCS: The control (UCHD) and intervention (EXHD) groups will be compared on the primary outcome measure (change from baseline to 6 months in KDQOL-SF 1.3 PCS) using a normal linear model adjusting for baseline KDQOL-SF 1.3 PCS. The findings will be presented as the (adjusted) mean difference (95% confidence interval) between the treatment groups

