6.6 Sample Size Calculation

A total of 380 patients will be randomised equally in the 5 centres to either UCHD or EXHD, giving 190 per treatment arm. Based on evidence from phase II trials (23) we expect 17-25% of patients to discontinue the exercise programme due to transplant, death or personal choice over the 9 month intervention period. A similar discontinuation rate will occur in the UCHD group, leading to 133 patients per group completing the study. Based on the PCS variability seen in Painter et al (31) and comparing 6-month KDQOL PCS between groups by two sample t-test (two-sided 5% significance level), this sample size would give 83% power to detect a mean difference of 4 points in KDQOL PCS. Greater power would be achieved in the final trial analysis through adjustment for baseline KDQOLPCS using analysis of covariance (ANCOVA). The 4 point effect size is of clinical relevance: as there is an established relationship between each 1 point increase in PCS and reduced mortality and hospitalisation (8,9). Such effect sizes have been reported for HD patients with a 7-point increase in the mean PCS of low functioning patients observed after an exercise training intervention (33).

7. Data Handling & Record Keeping

It is the responsibility of the PI (in conjunction with the Research Coordinator and RA) to ensure the accuracy of all data entered and recorded in the electronic CRFs and the database. The Delegation of Responsibilities Log will identify all trial personnel responsible for data collection, entry, handling and managing the database. The data will be collected by the RA (who will be blinded to the treatment allocation) and/or the RC, either directly onto a paper CRF with subsequent transcription to the eCRF, or direct data entry onto the web based eCRF. Where there is electronic storage of non-identifiable data it will be on a password protected device and/or database.

The study questionnaires (e.g KDQOL and EQ-5D) will be completed at each assessment visit by the patient with the assistance of the research assistant, directly onto a paper format with subsequent transcription to the eCRF.If the participant does not attend the assessment, the questionnaires will be given to the participant during dialysis, and collected back by the physiotherapy assistant.

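### Section 6.6 describes equal randomisation in 5 centres, but no centre factor enters the minimisation or the stated models; the cost is a small loss of precision, not bias

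*Protocol*

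**What the plan says.** Four places in the Protocol bear on this.

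- **Section 6.6 (sample size):** "A total of 380 patients will be randomised equally in the 5 centres to either UCHD or EXHD, giving 190 per treatment arm".
- **Section 4.4 (allocation):** "a minimisation algorithm will be employed, using baseline age, sex and diabetic status". No other balancing or stratification factor is named.
- **Section 6 (opening paragraph) and section 6.1 (primary outcome):** "All treatment comparisons will be adjusted for the minimisation variables (diabetic status, age and gender"). Section 6.1 adds baseline PCS for the primary outcome, "using a normal linear model adjusting for baseline KDQOL-SF 1.3 PCS". No centre, site or region term is stated, fixed or random.
- **Section 2.2 (design):** recruitment is in units "based in 10 sites across 5 regions of the United Kingdom". Section 4.1 agrees, with about 10 sites grouped into five regions. Section 3.1 gives only the overall split of 190 and 190.

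**The concern.** On its plain reading, section 6.6 claims 1:1 allocation inside each centre. Section 4.4 describes a procedure that does not look at centre, so balance by centre is left to chance.

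Centre could plausibly matter in this trial. Section 4.5.2 organises delivery by region: "We propose to employ physiotherapy assistants (PA, band 4 technical Instructors) in each region to deliver the intra-dialytic intervention". The exercise protocols come from a regional research assistant. Section 7 has the quality-of-life questionnaires completed with a research assistant's help, or collected by the physiotherapy assistant when a visit is missed. The type of patient and the content of usual care may also differ between units.

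Two things are at stake. The protocol claims a design property that its own method does not supply. And between-centre variation in PCS stays in the residual, although centre is known for every patient and could be adjusted for at almost no cost.

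**Working it through.** **1. The plan's own power figure.** Section 6.6 gives 133 completers per arm, a 4-point difference, a two-sided 5% two-sample t-test and 83% power. It cites a published trial for the SD but prints no number, so 83% can only be solved backwards:

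SD = 4 / [(1.960 + 0.954) × √(2/133)] = 4 / (2.914 × 0.1226) = 11.19 (11.15 with the noncentral t).

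With SD 11.19, the standard error of the difference is 11.19 × 0.1226 = 1.37. This is consistent with the stated power but is not independent confirmation of it.

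**2. Does the stated scheme give equal arms within centres?** Assume equal centre sizes (the protocol gives none), allocation unrelated to centre, and an overall split of exactly 190:190. The exercise-arm count in a centre is then hypergeometric.

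| Unit | Patients | 95% range in the exercise arm | Chance that at least one unit is split 60:40 or worse |
|---|---|---|---|
| 5 regions | 380/5 = 76 each | 30 to 46 | 23% |
| 10 sites | 380/10 = 38 each | 13 to 25 | 91% |

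Across 5 regions, the largest arm difference has a median of 12 patients and a 95th percentile of 20. If the overall split is not fixed, Binomial(76, 0.5) gives 29 to 47 and Binomial(38, 0.5) gives 13 to 25, so the picture is the same. Equal allocation within each centre does not follow from section 4.4.

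These are head-counts. They do not measure error in the treatment estimate.

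**3. What leaving centre out of the model costs.** The protocol gives no between-centre variance, so the intraclass correlation (ICC) is assumed over 0.01 to 0.10. A centre term reduces the residual SD to 11.19 × √(1 − ICC). Power is then Φ(4 / [SD × √(2/133)] − 1.960).

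| Assumed ICC | Residual SD | Power with 133 per arm | n per arm for 83% power |
|---|---|---|---|
| 0 | 11.19 | 83.0% | 133 |
| 0.01 | 11.14 | 83.4% | 132 |
| 0.02 | 11.08 | 83.7% | 131 |
| 0.05 | 10.91 | 84.8% | 127 |
| 0.10 | 10.62 | 86.7% | 120 |

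The gain is 0.4 to 3.7 power points. The calculation ignores the few degrees of freedom spent on the term, which are negligible with 266 evaluable patients.

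**4. Does the omission harm validity?** The part of the estimate's SD that comes from chance imbalance by centre is 11.19 × √ICC × √(2/133). At ICC 0.02 this is 0.19 points, and at 0.07 it is 0.36, against a total standard error of 1.37 that already includes it. Simulating 133 per arm in 10 sites with ICC 0.05 and no site term gave a type I error of 4.8% to 5.0%, which is nominal.

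**The case against.** The strongest reply has three parts.

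**The sentence in 6.6 may be loose wording.** It stands in the sample-size section, ends with 190 per arm, and may mean no more than overall 1:1 allocation. Section 4.4 is the operative text and is clear. This reading is possible. Even so, 6.6 would still need rewording, because 5 centres and 10 sites in 5 regions cannot both describe the same units.

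**A centre term is often left to the statistical analysis plan.** That plan is not shown, and the covariate list in section 6 is not closed, since section 6.1 adds baseline PCS. But the protocol is not silent. It states which adjusters apply to every treatment comparison, and centre is not among them. An analysis plan could add the term. It could not alter how patients were allocated or correct 6.6.

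**The gain is small and partly captured already.** Baseline PCS, age, sex and diabetic status should absorb much of any stable difference between centres. The ICC that matters is the one left after that adjustment, which is probably nearer 0.01 than 0.10. This stands.

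A reader might also infer that chance imbalance by site confounds the result or undermines the test. The documents do not support that. Allocation is by individual, so the estimate is unbiased in expectation, and chance imbalance is already carried in the standard error. The high probability of an uneven split somewhere shows only that 6.6 overstates what the design delivers.

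**Conclusion.** The point holds as an inconsistency with a modest cost. Section 6.6 claims balance within centres that section 4.4 does not provide, and it counts centres differently from sections 2.2 and 4.1. Omitting centre from the stated adjusters gives up about 0.4 to 3.7 power points on the planned 83%, with the low end more likely. It does not threaten the validity of the primary comparison.

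The precision figures rest on an assumed ICC of 0.01 to 0.10 and a back-solved SD of about 11.2. The imbalance figures assume equal centre sizes. The textual inconsistency depends on none of these.

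**What to change.** - **Analysis (section 6):** add region as a fixed effect, or site as a random intercept, to the adjusters stated for the treatment comparisons. State which one before unblinding, so that the choice cannot depend on any imbalance seen. Cost: 4 degrees of freedom for region, or one variance component for site. No new data are needed.
- **Wording (section 6.6):** replace the claim of equal randomisation in 5 centres with overall 1:1 allocation across 5 regions and about 10 sites, and use the same terms throughout.
- **Allocation (section 4.4), as the alternative to rewording the balance claim:** add region or site to the minimisation, but only if randomisation is still open. Section 2.2 plans recruitment to July 2016, the protocol declaration refers to Version 3.0 of November 2016, and Appendix 7 still mentions a third wave, so the document does not settle this. Cost: a setting in the web randomisation system and an amendment. If recruitment has closed, the model term and the wording are enough.
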